11. MANAGEMENT AND REPORTING OF ADVERSE EVENTS/ADVERSE REACTIONS

In this study, data will be collected by the following two methods 1) Human review of Unstructured Data, and 2) Survey of patients to assess HRQoL. AEs and SAEs reporting requirement for both methods are described below.

11.1. Human Review of Unstructured Data

This study protocol requires human review of patient-level unstructured data; unstructured data refer to verbatim medical data, including text-based descriptions and visual depictions of medical information, such as medical records, images of physician notes, neurological scans, x-rays, or narrative fields in a database. The reviewer is obligated to report adverse events (AEs) with explicit attribution to any Pfizer drug that appear in the reviewed information (defined per the patient population and study period specified in the protocol). Explicit attribution is not inferred by a temporal relationship between drug administration and an AE but must be based on a definite statement of causality by a healthcare provider linking drug administration to the AE.

The requirements for reporting safety events on NIS AE Report Form for Protocols with Stipulated Active Collection of AEs to Pfizer Safety are as follows:

- All serious and non-serious AEs with explicit attribution to any Pfizer drug that appear in the reviewed information must be reported, within 24 hours of awareness, to Pfizer Safety using the NIS AEM Report Form.
- Scenarios involving drug exposure, including exposure during pregnancy, exposure during breast feeding, medication error, overdose, misuse, extravasation, lack of efficacy, and occupational exposure associated with the use of a Pfizer product must be reported, within 24 hours of awareness, to Pfizer Safety using the NIS AEM Report Form.
- If an embryo or fetus has been exposed to the study drug, as soon as exposure during pregnancy (EDP) has been diagnosed, send the EDP supplemental form with the NIS AEM Report Form with the appropriate fields completed.
- For these AEs with an explicit attribution or scenarios involving exposure to a Pfizer product, the safety information identified in the unstructured data reviewed is captured in the Event Narrative section of the report form, and constitutes all clinical information known regarding these AEs. No follow-up on related AEs will be conducted.

All the demographic fields on the NIS AEM Report Form may not necessarily be completed, as the form designates, since not all elements will be available due to privacy concerns with the use of secondary data sources. While not all demographic fields will be completed, at the very least, at least one patient identifier (eg, gender, age as captured in the narrative field of

the form) will be reported on the NIS AEM Report Form, thus allowing the report to be considered a valid one in accordance with pharmacovigilance legislation. All identifiers will be limited to generalities, such as the statement “A 35-year-old female...” or “An elderly male...” Other identifiers will have been removed.

Additionally, the onset/start dates and stop dates for “Illness,” “Study Drug,” and “Drug Name” may be documented in month/year (mmm/yyyy) format rather than identifying the actual date of occurrence within the month /year of occurrence in the day/month/year (DD/MMM/YYYY) format.”

11.2. Patients Survey Assessing HRQoL

This study does not involve data collection on individual patients by their treating healthcare professionals and the questionnaires used in this study do not intend to identify product safety information. However, the questionnaire will be completed by participants online and via paper-based questionnaire, and a participant could volunteer product safety information in free text fields, in blank margins, to study personals, etc. Any safety information for an individual patient that is volunteered by a study participant (e.g., the patient him/herself, health care professional, lay person) during this research must be reported as described below:

The following safety events must be reported on the NIS AE Report from for Protocols without stipulated active collection: serious and non-serious adverse events (AEs) when associated with the use of the Pfizer product, and scenarios involving exposure during pregnancy, exposure during breast feeding, medication error, overdose, misuse, extravasation, lack of efficacy and occupational exposure (all reportable, regardless of whether associated with an AE), when associated with the use of a Pfizer product.

In the event that a study participant volunteers product safety information, study site staff must complete the NIS AE Report from for Protocols without stipulated active collection of AEs and submit to Pfizer within 24 hours of becoming aware of the safety event. Included in the completion of the NIS AEM Report Form is the study participant’s contact information; complete contact information should be obtained so that, once the NIS AEM Report Form is sent to Pfizer, the NIS AEM Report Form can be assessed and processed according to Pfizer’s standard operating procedures, including requests for follow-up to the study participant.

11.3. Pfizer Training Requirements:

All research staff members must complete the following Pfizer training requirements:

- *“Your Reporting Responsibilities (YRR) with Supplemental Topics.”*

These trainings must be completed by research staff members prior to the start of data collection. All trainings include a “Confirmation of Training Statement” (for signature by the trainee) as a record of completion of the training, which must be kept in a retrievable format. Copies of all signed training statements must be provided to Pfizer.

Re-training must be completed on an annual basis using the most current Your Reporting Responsibilities (YRR) with Supplemental Topics training materials. Where Pfizer issues an updated safety training program, including during the course of a calendar year, vendor shall ensure all vendor personnel complete the updated safety training within sixty (60) calendar days of issuance by Pfizer.

11.4. Regulatory Agency, Institutional Review Board, and Site Reporting

The Sponsor and/or Clinical Research Organization (CRO) are responsible for notifying the relevant regulatory authorities, central Institutional Review Boards (IRBs), and study doctors of related, serious unexpected adverse reactions (SUSARs) as per local regulations. The study doctor is responsible for notifying the local IRBs of all SAEs that occur at his or her site as required by local regulations, if this responsibility resides with the study doctor.

12. PLANS FOR DISSEMINATING AND COMMUNICATING STUDY RESULTS

In the event of any prohibition or restriction imposed (eg, clinical hold) by an applicable competent authority in any area of the world, or if the investigator is aware of any new information which might influence the evaluation of the benefits and risks of a Pfizer product, Pfizer should be informed immediately.

12.1. Dissemination of Study Data

This study and study results will be posted on the US National Institutes of Health's website www.Clinicaltrials.gov and other publicly accessible sites.

12.2. Publication Policy

It is intended to publish the results of the study at regular time intervals (eg, yearly) over the course of the study. Authorship will be determined by the GBT Registry Steering Committee and in line with International Committee of Medical Journal Editors authorship requirements.

14. LIST OF TABLES

None.

15. LIST OF FIGURES

Figure 1: [Study Schema](#)

Figure 2: [Enrollment Process Flow](#)

ANNEX 1. LIST OF STANDALONE DOCUMENTS

None.

ANNEX 2. ENCEPP CHECKLIST FOR STUDY PROTOCOLS

Not required.

ANNEX 3. ADDITIONAL INFORMATION

Not applicable.

Appendix 1. Schedule of Activities

| Data Collection/Procedure | Pre-Oxbryta® (Voxelotol) treatment period | Study Data Collection Period | | | | | | | | | | | |
|---|---|------------------------------|---|---|----|----|----|----|----|----|----|----|----|
| | | 3 | 6 | 9 | 12 | 18 | 24 | 30 | 36 | 42 | 48 | 54 | 60 |
| Month Intervals | -12 to 1 | | | | | | | | | | | | |
| Informed Consent/Accent ^a | X | | | | | | | | | | | | |
| Review of eligibility ^b | X | | | | | | | | | | | | |
| Medical history and SCD genotype ^c | X | | | | | | | | | | | | |
| Physical examination (including height and weight) and vital signs ^d | X | X | X | X | X | X | X | X | X | X | X | X | X |
| Clinical outcomes and interventions ^e | X | X | X | X | X | X | X | X | X | X | X | X | X |
| Health resource utilization ^f | X | X | X | X | X | X | X | X | X | X | X | X | X |
| HRQoL assessments (PROMIS, NPRS, and exercise tolerance) ^g | X | X | X | X | X | X | X | X | X | X | X | X | X |
| CGIC and PGIC | | X | X | X | X | X | X | X | X | X | X | X | X |
| SCD medications ^h | X | X | X | X | X | X | X | X | X | X | X | X | X |
| Safety data ⁱ | X | X | X | X | X | X | X | X | X | X | X | X | X |
| Serum pregnancy test ^j | X | | | | | | | | | | | | |
| Urine pregnancy test ^k | | X | X | X | X | X | X | X | X | X | X | X | X |

CGIC=Clinical Global Impression of Change; HRQoL=Health-related quality of life; PGIC=Patient Global Impression of Change; PROMIS=Patient-Reported Outcomes Measurement Information System; NPRS=Numerical Pain Rating Scale.

NOTE: With the exception of informed consent/assent, all other data listed above are required to be collected if assessments are performed as part of the participant's standard-of-care; the data from these assessments will be collected at the timepoints indicated (if available) and will include all data available for the period between the timepoints.

- A signed and dated consent and/or assent form (age <18 years) will be obtained before any data collection for the study. For pediatric participants, consent should be obtained from at least one parent (or both if it is required per investigational site policy) or the participant's legally authorized representative.
- Inclusion and exclusion criteria should be reviewed at the pre-Oxbryta® (Voxelotol) treatment period to ensure participant eligibility is met.
- Record available significant medical history for up to 12 months prior to the first dose of Oxbryta® (Voxelotol) (retrospective data) in the CRF. Record demographics (sex, race, ethnicity, and age), and SCD characteristics (including hematological parameters), using the most recent data before enrollment. Record all available SCD genotype results. Perform SCD genotype (at pre-Oxbryta® (Voxelotol) treatment period) only for a medical diagnosis of SCD, if diagnosis is not documented in medical chart.

- d. Physical examination (including height and weight) will be collected at the screening visit for all participants 18 and above, and at screening and all follow up visits for participants up to age 18. Pulse oximetry [%SpO₂] will be collected for all participants at screening and all follow up visits per standard of care.
- e. Record available clinical outcomes data including laboratory assessments, for example: VOCs, ACS, priapism, stroke, TIAs, leg ulcers, cardiac malfunction, pulmonary hypertension, RBC transfusions, and SCD-related medication use (see [Section 10.3.6.1](#) for details).
- f. Health resource utilization includes any outpatient visits (including infusion center, acute care, or telemedicine visit), ED visits, hospitalizations (including length of stay, if applicable), acute and chronic RBC transfusions, home oxygen supplementation, and renal dialysis occurring during the period between data collection timepoints.
- g. HRQoL assessments will include PROMIS, PGIC, NPRS, CGIC, and exercise tolerance. Record data from the most recent assessment before each collection timepoint. If not performed as part of the participant's usual care, the questionnaires will be provided for the participant, parent/caregiver, or clinician to complete. See [Section 10.3.6.3](#) for details. The questionnaires are provided in [Appendix 2](#).
- h. Record medications for SCD-related conditions (eg, hydroxyurea, crizanlizumab, L-glutamine, opioids, in daily morphine equivalents, iron chelating agents, ESAs, NSAIDs, folic acid, and penicillin) taken by the participant from 12 months before screening through the end of study participation (5 years after the first dose of Oxbryta® (Voxelotor) treatment or early discontinuation).
- i. Record all serious adverse events, adverse events of interest, Oxbryta® (Voxelotor)-related AEs, other safety events, pregnancy test results, and reports of fertility issues occurring during the period since the last collection timepoint. See [Section 11](#) for definitions and for details on recoding and reporting AEs and safety events.
- j. Females of child-bearing potential will have a serum pregnancy test at Screening.
- k. Urine pregnancy tests will be performed at scheduled visits for females of child-bearing potential. If a urine pregnancy test is positive, the result must be confirmed with a serum pregnancy test. See [Section 11](#).

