| Statistical Methods | 
Analysis Population Effectiveness and safety analyses will primarily be based on the treated population, defined as all participants receiving at least one dose of Oxbryta® (Voxelotor).
 
Sample Size The sample size is selected to provide an estimation of the relationship between change in Hb and significant clinical events, for example VOCs, stroke, TIA, and PH that participants experience over the 5 years of the study. The total sample size of approximately 750 participants is expected to be enrolled in the study.
 
Effectiveness Analyses Change from pre-Oxbryta® (Voxelotor) treatment period in Hb, hemolysis measures, measures of iron overload, and renal function over time will be summarized descriptively. Annualized rate of significant SCD-related clinical events, for example VOC, ACS, priapism, stroke, TIA, chronic or end stage kidney disease, iron overload, leg ulcers, cardiac malfunction, PH, and RBC transfusions will be calculated. The association between change in Hb and hemolysis marker and rates of SCD-related clinical events will be evaluated. Rates of outpatient visits (including infusion center, acute care, or telemedicine visit), ED visits, hospitalizations, acute and chronic RBC transfusions, home oxygen supplementation, and renal dialysis will be summarized with a similar approach as rate of SCD-related clinical events. The total cost associated with clinical interventions will be summarized descriptively. HRQoL measures over time will be summarized descriptively. Proportion of participants with improved HRQoL measures will be calculated and the associated 95% Clopper -Pearson Exact confidence intervals will be constructed as appropriate. As appropriate, rates of SCD-related clinical events, healthcare resource utilization, total cost associated with clinical interventions (if available) and HRQoL while on Oxbryta® (Voxelotor) treatment will be compared with the corresponding measures in the 12 months prior to the first dose of Oxbryta® (Voxelotor) treatment. Similar comparisons may be performed between the subgroup of participants who discontinue Oxbryta® (Voxelotor) treatment but remain in the study and those participants who remain on Oxbryta® (Voxelotor).
 
Safety Analysis SAEs and protocol-specified AEs will be classified according to Medical Dictionary for Regulatory Activities (MedDRA). The total number with percentage and severity of AEs will be tabulated by system organ class and
 |

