10.3.6.1.2. SCD Complications

For the pre Oxbryta® (Voxelotor) treatment SCD complications, all events that occurred within 12 months prior to starting Oxbryta® (Voxelotor) treatment will be recorded in the CRF.

For the post- Oxbryta® (Voxelotor) treatment SCD complications, all events occurring since the last collection timepoint will be recorded in the CRF.

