4.3. Variables

Variable	Role	Data source(s)	Operational definition
Index date	Study period	Case report form	Inform consent date
Index year	Study period	Case report form	Inform consent date
Pre-Oxbryta	Study period	Case report form	Baseline: any assessments within 12 months before receiving first dose of Oxbryta® (Voxelotor)
Post-Oxbryta	Study period	Case report form	Follow-up period for up to 5 years after the first dose of Oxbryta® (Voxelotor)
End of Treatment	Study period	Case report form	Captured from end of treatment form
End of Study	Study period	Case report form	Captured from end of study form
Age	Demographics	Case report form	Age at first dose of Oxbryta
Sex	Demographics	Case report form	Captured from the inform consent and eligibility form
Race/Ethnicity	Demographics	Case report form	Captured from the inform consent and eligibility form

SCD genotype	SCD disease history	Case report form	Captured from SCD disease history form
Hydroxyurea use	SCD disease history	Case report form	Captured from SCD disease history form
Height	Baseline characteristics	Case report form	Captured from Physical examination form
Weight	Baseline characteristics	Case report form	Captured from Physical examination form
Pre-Oxbryta SCD complications	Medical history	Case report form	Captured from Pre-Oxbryta treatment form
Concomitant Medications	Concomitant Medications	Case report form	Captured from concomitant medications form
Hemoglobin	Effectiveness endpoint measures - Hematology	Case report form	Captured from laboratory assessment-Hematology form
Reticulocyte count (%)	Effectiveness endpoint measures - Hematology	Case report form	Captured from laboratory assessment-Hematology form
Reticulocyte count (absolute)	Effectiveness endpoint measures - Hematology	Case report form	Captured from laboratory assessment-Hematology form
White blood cells (WBC)	Effectiveness endpoint measures - Hematology	Case report form	Captured from laboratory assessment-Hematology form
Aspartate Aminotransferase (AST)	Effectiveness endpoint measures - Hematology	Case report form	Captured from laboratory assessment-Hematology form
Alanine Aminotransferase (ALT)	Effectiveness endpoint measures - Hematology	Case report form	Captured from laboratory assessment-Hematology form
Bilirubin (Total)	Effectiveness endpoint measures - Chemistry	Case report form	Captured from laboratory assessment-Chemistry form

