4.7.4. Safety analysis

SCD complications are defined as 'Yes' to the question 'is this a SCD Complication' in the SCD complications/AE form while the other AEs are defined as 'No' to the question 'is this a SCD Complication' in the SCD complications/AE form.

All safety analyses will be based on safety analysis set (Section 4.2). The analysis period for Pre-Oxbryta is 12 months before the first dose of Oxbryta and the analysis period for post-Oxbryta is from the first dose of Oxbryta through end of the study or the date of dose pausing or treatment discontinuation if the date of end of study date is missing.

SAEs and protocol-specified AEs will be classified according to the Medical Dictionary for Regulatory Activities (MedDRA). The frequency of SCD complications and other AEs treatment-emergent adverse events (TEAEs) and treatment emergent SAEs will be tabulated by system organ class, preferred term, severity (and total), and relationship to Oxbryta® (Voxelotor) treatment. The pregnancy outcomes and fertility will be reported as a listing. Any events (including deaths) leading to discontinuation of the study and SAEs will be listed.

A TEAE is defined as an AE that occurs during the effective duration of treatment defined as the time from the first dose of Oxbryta through end of treatment date or the end of study completion/discontinuation date (if the date of end of treatment is missing) +28 days.

On the AE case report form there is a question “Did AE start prior to first dose?”

- If the response is “Yes” or the adverse event start date is missing, and the end date is prior to the first dose of Oxbryta, then the AE is not considered a TEAE
- If the response is “No” or “Unknown”, then the AE is considered a TEAE

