4.7.5. Subgroup analyses

Analysis: The annualized incidence rate (per patient year) of rate of ‘Acute Pain Crisis’ (SCD Complications) will be performed by Pre-Oxbryta and Post-Oxbryta.

Analysis subgroups:

- Chronic pain
 - a. participants with chronic pain
 - b. participants without chronic pain
- Maximum increase from Pre-Oxbryta in Hb
 - a. Full analysis set for participants with > 1 g/dL maximum increase from Pre-Oxbryta in Hb
 - b. Full analysis set for participants with <= 1 g/dL maximum increase from Pre-Oxbryta in Hb

Analysis: Annualized incidence VOC rate for pre-Oxbryta and post-Oxbryta will be reported.

The VOC event for Pre-Oxbryta is defined as 1) SCD complication with ‘Acute Pain Crisis’ in the Pre-Oxbryta SCD complication page or 2) any qualifying complications from SCD AE prior to Treatment Start Date.

The VOC event for Post-Oxbryta is defined as any qualifying complications from SCD AE on or after the treatment start date.

The qualifying complications from SCD AE are those that met at least one of the following two conditions:

- AE preferred term (AEDECOD) to be 'Sickle cell anaemia crisis';
- type of complications (CMPTYP) is 'Acute Pain Crisis'

- 1) Analysis population: Safety analysis set where participants had a non-missing Pre-Oxbryta SCD complications will be included in the analysis.
- 2) Analysis population: Safety analysis set where participants who had a non-missing Pre-Oxbryta SCD complications or participants who had an adverse events reported in Pre-Oxbryta or Post-Oxbryta will be included in the analysis.

Analysis: The annualized VOC incidence rate (per patient year) will be performed by Pre-Oxbryta and Post-Oxbryta.

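### Protocol Appendix 1 prints the pre-Oxbryta window as running to month 1, against a first-dose cut elsewhere, and the SAP crisis rule has no date condition that would catch a misfiled event

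*Protocol*

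**What the plan says.** The pre-treatment column of the Protocol Appendix 1 schedule is headed "Month Intervals | -12 to 1". Protocol 9.7 points sites to this schedule for which items to enter and when. The row for clinical outcomes, which by footnote e includes vaso-occlusive crises (VOCs), is marked in that column.

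The other definitions stop at first dose:

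- Protocol Appendix 1, footnote c: "Record available significant medical history for up to 12 months prior to the first dose".
- Protocol 10.3.6.1.2, on sickle cell complications: "all events that occurred within 12 months prior to starting Oxbryta® (Voxelotor) treatment will be recorded in the CRF".
- Protocol abstract, on the comparison period: "in the 12 months prior to the first dose of Oxbryta® (Voxelotor) treatment".
- SAP 4.3, defining Pre-Oxbryta: "any assessments within 12 months before receiving first dose".
- SAP 4.7.4: "The analysis period for Pre-Oxbryta is 12 months before the first dose of Oxbryta".
- SAP 4.7.1 starts the post period at first dose.

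SAP 4.7.5 gives two routes by which a crisis becomes a pre-treatment VOC: an Acute Pain Crisis "in the Pre-Oxbryta SCD complication page or 2) any qualifying complications from SCD AE prior to Treatment Start Date". Post-treatment VOCs come only from the adverse event (AE) form, dated from treatment start onward.

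**The concern.** A site that took the column header at face value could enter a crisis from the first month on drug on the Pre-Oxbryta page. The opportunity is plainest for participants already on drug at consent, because for them that month lies in the past when the page is completed. SAP 4.7.5 would then count the event as pre-treatment because of the page it is on. Thirteen months of events would be set against a 12-month period, and the before-and-after crisis rates (Tables 15.5.1 to 15.5.5) would shift in the drug's favour with no drug effect. These rates are the plan's main before-and-after contrast for crises, so the pre/post boundary should rest on dates and not on which form was used.

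**Working it through.** **Step 1. Is there a conflict?** Yes, on the printed text. The header ends at month 1, while the six other places listed above end the pre period, or start the post period, at first dose.

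**Step 2. Would the analysis rule remove a misfiled event?** The date limits written into the VOC rules of SAP 4.7.5 are:

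| Route | Upper date limit | Lower date limit |
|---|---|---|
| Pre-Oxbryta page, counted as pre | none written | none written |
| AE form, counted as pre | before treatment start | none written |
| AE form, counted as post | none written in the rule | treatment start |

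A first-month crisis on the Pre-Oxbryta page therefore counts as pre. It counts as post only if it is also entered on the AE form, in which case it is counted twice. By its own wording, the second route also admits an AE-form event more than 12 months before first dose. Nothing in the documents shows how many such events exist, so this part is not sized.

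**Step 3. What is the denominator?** SAP 4.7 divides total events by total patient-years and takes duration from SAP 4.7.1, which defines only the post period. Twelve months for the pre period is inferred from SAP 4.7.4.

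**Step 4. How large could the effect be?** The documents state no crisis rate and no size for this effect, so there is no figure of the plan's to reproduce. Let f be the share of first-month crises misfiled as pre, and R the ratio of the on-drug rate to the pre rate. Both are assumptions. With a constant rate within each period and a 12-month denominator:

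rise in pre rate = (12 + f × R)/12 − 1 = f × R/12

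| f | R = 1.0 | R = 0.75 | R = 0.5 |
|---|---|---|---|
| 1.0 | 8.3% | 6.3% | 4.2% |
| 0.5 | 4.2% | 3.1% | 2.1% |
| 0.1 | 0.8% | 0.6% | 0.4% |

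For example, f = 1 and R = 1 gives 13/12 − 1 = 8.3%, and f = 0.1 and R = 1 gives 0.1/12 = 0.8%. If sites follow Protocol 10.3.6.1.2, f = 0 and the rise is zero.

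**Step 5. Does the denominator matter?** Yes. If the pre period were also counted as 13 months, then f = 1 and R = 1 gives 13/13 = 1, with no rise. No passage gives a 13-month period, but the result shows why the denominator should be stated.

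**The case against.** The strongest reply is that the documents correct the header themselves. The column is titled as the pre-treatment period. Footnote e, which covers crises, refers sites to Protocol 10.3.6.1, and 10.3.6.1.2 stops at the start of drug. In the SAP, Pre-Oxbryta is a defined term with a 12-month limit in 4.3 and 4.7.4, and 4.7.5 can be read as inheriting that limit. A site would have to follow a column header over the section its own footnote cites. This largely stands: it is why misfiling is not the expected outcome. It does not close the gap, because the page route is an explicit counting rule with no date test, and a programmer following it would not remove a misfiled event.

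The header may also have lost a minus sign. A reader might then infer that a window of −12 to −1 drops the month before first dose and leaves 11 months. The documents do not support that: the row counts month intervals, and intervals −12 through −1 can be read as twelve months, the last ending at first dose. On that reading the header agrees with the other passages, and only the SAP rule needs attention.

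A reader might further infer that first-month laboratory values could become the baseline. Protocol 9.4 takes the latest observation before drug and SAP 4.3 takes assessments before first dose; a first-month value meets neither definition.

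**Conclusion.** The point holds as an inconsistency with a missing safeguard. The printed header conflicts with the first-dose cut used elsewhere, and the VOC rule would not detect the error if a site followed the header. The rise in the pre rate is at most 8.3%, assuming a constant crisis rate, no drug effect, every first-month crisis misfiled and a 12-month denominator. At 10% misfiling it is about 0.8%.

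Two stronger conclusions are not supported. One is that the pre-treatment rate is in fact inflated: nothing shows that any site has misfiled a crisis, and the recording rules say not to. The other is that the post/pre ratio would fall to about 0.85. That figure is (11/12)/(13/12) = 0.846, and on top of the assumptions above it needs exactly one post year and no misfiled crisis re-entered as a post event. Yet Protocol 10.3.6.1.2 asks for every event since the previous collection timepoint. It stacks worst cases and should not be quoted as an expected bias.

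**What to change.** 1. In Protocol Appendix 1, reword the header as the 12 months ending the day before first dose.
2. In SAP 4.7.5, count a crisis as pre-Oxbryta only if its onset falls in that interval, and as post-Oxbryta if its onset is on or after first dose, whichever form it is on. This also supplies the missing lower limit on the AE-form route.
3. In the SAP, state 12 months as the pre-period denominator, since SAP 4.7.1 does not define it.
4. Run a date check on entries already on the Pre-Oxbryta page.

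The cost is one table header, a short SAP clause and one programmed check. The small downside is that the documents do not show whether the Pre-Oxbryta page records onset dates. If it does not, some entries will need site queries.
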